4.15 Biomarkers

Descriptive statistics for observed values, changes from baseline and % changes from baseline, and a by-patient listing will be provided for the following biomarkers based on Exploratory Population. This data will also be displayed graphically as appropriate.

Biomarker	Description	Read out*					
MMP-3	Matrix metalloprotei	nase-3					
GM-CSF	Granulocyte mac	ophage colony					
	stimulating factor						
CXCL10	C-X-C motif chemok	ine ligand 10					
CCL2	C-C motif chemokine	C-C motif chemokine ligand 2					
COMP	Cartilage oligomeric	Cartilage oligomeric matrix protein					
TNF-α	Tumor necrosis facto	Tumor necrosis factor - α					
TNF-RI	Tumor necrosis facto	Tumor necrosis factor-RI					
IL-6	Interleukin-6	Interleukin-6					

* Biomarker name exactly as it will appear in the dataset

Handling of LLOQ and ULOQ

Biomarker data are reported as concentration results, measured using a specific assay with a working range defined by the two limits: Lower limit of quantification (LLOQ) and Upper limit of quantification (ULOQ). Values which fall below the LLOQ or above the ULOQ are reported as < LLOQ * dilution factor (dilution factor: if sample diluted and concentration measured still below LLOQ) and > ULOQ * dilution factor, respectively.

To ensure that biomarkers only have numerical values, censored values will be imputed as follows

- Values below the LLOQ are replaced by LLOQ/2.
- Values above the ULOQ are replaced by ULOQ.

Imputed values are used for summary statistics, inferential analyses and plots (with a special symbol). Values below LLOQ and values above ULOQ are shown as such in the listings. In the

summary table, the frequency (n, %) of values below the LLOQ and above the ULOQ, respectively, will be included.

If the proportion of imputed data is more than 20% for any treatment group at any time point, a footnote is added to the summary statistics table stating that the proportion of values outside the limits of quantification is more than 20% for some treatment groups at some time points and that in such cases summary statistics may be heavily biased.

If the proportion of imputed data for a given biomarker, across all treatment groups and time points, is more than 50%, no summary statistics will be provided, and the data are only listed.

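### SAP 4.15 reports out-of-range biomarker results at the limit times the dilution factor but imputes them at the undiluted limit, so a diluted sample above range is scored below its known lower bound

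*SAP*

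**What the plan says.** SAP 4.15 (Biomarkers, handling of LLOQ and ULOQ) takes three steps.

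- **Definition.** Concentrations are "measured using a specific assay with a working range defined by the two limits", namely LLOQ and ULOQ. No dilution factor enters this definition.
- **Reporting.** "Values which fall below the LLOQ or above the ULOQ are reported as < LLOQ * dilution factor" and, at the high end, as "> ULOQ * dilution factor, respectively". A parenthesis in the same sentence explains that this covers a sample that was diluted and still read below the limit, so the SAP expects diluted samples.
- **Imputation.** "Values below the LLOQ are replaced by LLOQ/2" and "Values above the ULOQ are replaced by ULOQ". Neither rule carries the dilution factor.

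The imputed values then feed the tables and plots. The section plans "Descriptive statistics for observed values, changes from baseline and % changes from baseline". Out-of-range results keep their reported form only in the listings. The summary table also gives the number and percentage below LLOQ and above ULOQ, and imputed points get their own plot symbol. A warning is tied to a threshold: "If the proportion of imputed data is more than 20% for any treatment group at any time point, a footnote is added". If more than 50% of a biomarker's values over all groups and time points are imputed, its summary statistics are dropped.

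Biomarker blood is drawn before dosing on Day 1 and again on Day 7 (protocol 1.3, Schedule of Activities). Each cohort has 6 active and 2 placebo patients (SAP 3.1), and SAP 4.2.1 lists a pooled placebo group.

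**The concern.** Within one section, the limit carries the dilution factor when a result is reported and loses it when the result is imputed. A programmer who follows the two bullets literally will use the undiluted limit.

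At the high end this produces a value that the laboratory report rules out. The result is known to lie above ULOQ × DF and is entered as ULOQ. A diluted sample that reads in range keeps its full value, which can be anything up to ULOQ × DF. A measured value can therefore outrank a censored one that is known to be higher.

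The effect of TCK-276 on these biomarkers is the exploratory objective, and each patient contributes one baseline and one on-treatment value. With 6 active patients per cohort, one value on the wrong scale changes that patient's direction or size of change and moves the cohort mean, SD and percent change.

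**Working it through.** The plan gives no worked biomarker figure, so there is nothing to reproduce. The check applies the two written rules and compares them with imputation at the sample's own limit.

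**Inputs**

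- Reporting and imputation rules: SAP 4.15.
- Arm size: 6 active per cohort (SAP 3.1); pooled placebo 4 × 2 = 8 (SAP 4.2.1).
- DF: not in the documents, nor are any LLOQ or ULOQ values. DF is an assumption, varied from 1 to 50.
- Percent change is taken as (Day 7 − Day 1)/Day 1. SAP 4.15 does not define the sign. SAP 4.13.8 uses Day 1 − Day 7 for disease activity; with that sign the printed direction would be just as wrong.

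**High side, one patient.** Day 1 is measured in range at b × ULOQ (in a diluted sample if b is above 1). Day 7 is reported as above DF × ULOQ.

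- As written: (1 − b)/b.
- Smallest change compatible with the report: (DF − b)/b.

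| DF (assumed) | Day 1, × ULOQ | As written | At least |
|---|---|---|---|
| 1 | 0.5 | +100% | +100% |
| 2 | 1.5 | (1 − 1.5)/1.5 = −33.3% | (2 − 1.5)/1.5 = +33.3% |
| 4 | 2 | (1 − 2)/2 = −50% | (4 − 2)/2 = +100% |
| 10 | 5 | (1 − 5)/5 = −80% | (10 − 5)/5 = +100% |
| 50 | 25 | (1 − 25)/25 = −96% | (50 − 25)/25 = +100% |
| 10 | 0.5 | (1 − 0.5)/0.5 = +100% | (10 − 0.5)/0.5 = +1900% |

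The written rule gives a negative sign exactly when b is above 1, while the true change is positive because b is below DF. So the sign reverses for 1 < b < DF. For b below 1 the sign is right and the rise is understated. At DF = 1 the two rules agree.

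The mirror case follows from the same rule. With DF 10, a Day 1 result above 10 × ULOQ and a Day 7 value measured at 5 × ULOQ is a fall of at least (10 − 5)/10 = 50%. As written it becomes (5 − 1)/1 = +400%.

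**High side, one cohort of 6.** Assume DF 10, all six at 5 × ULOQ on Day 1, five unchanged on Day 7 and one reported above 10 × ULOQ.

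- As written: mean percent change (5 × 0 − 80)/6 = −13.3%.
- At the sample's own limit: (5 × 0 + 100)/6 = +16.7%, a lower bound.

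**Low side.** A result reported as below LLOQ × DF is set to LLOQ/2. Half of the sample's own limit is (LLOQ × DF)/2. The ratio is DF: at DF 2, 0.5 against 1 × LLOQ; at DF 10, 0.5 against 5 × LLOQ. LLOQ/2 is always below LLOQ × DF, so it does not conflict with the report.

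**Footnote.** One imputed value is 1/6 = 16.7% of an active arm and 1/8 = 12.5% of pooled placebo. Both are under 20%, so no footnote appears. If placebo were shown by cohort, 1/2 = 50% would trigger it there, but not in the active arms.

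**The case against.** The best defence is that the bullets are shorthand. They follow directly on the reporting sentence, so ULOQ could mean the limit that applies to that sample. SAP 4.13.3 supports this: safety laboratory results given with a less-than or greater-than sign are imputed with the reported number itself, which would keep the scale. But that rule covers clinical laboratory tests, and SAP 4.15 sets its own rule for biomarkers. The section writes the dilution factor when it means the scaled limit and leaves it out of the imputation rules. The authors may have intended the scaled limit; the text does not say so.

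The second defence is transparency. The out-of-range counts have no threshold, imputed points are marked in plots, and the listings show the reported result. With 32 patients and two time points, a careful reader could trace a case. This stands as far as it goes: the safeguards show that a value was censored. They do not show that it was entered on the wrong scale, and they do not correct the table.

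Some stronger readings are tempting, and the documents do not support them.

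- A reader might infer that every diluted sample above range is ranked below lower measured ones, or that every such rise prints as a fall. Either needs a comparison value between 1 × ULOQ and DF × ULOQ.
- A reader might infer that the low-side rule also contradicts the report. It does not: LLOQ/2 lies inside the censored interval, and at the same DF it does not reverse the order, because in-range diluted samples read at least LLOQ × DF.
- A reader might take −80% against +100% as the expected error. It rests on an assumed DF of 10. Nothing in the documents says how often any of the eight biomarkers will be diluted and still be out of range.

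**Conclusion.** The point holds on the text as written. For any DF above 1, the high-side rule enters a value below the lower bound that the report establishes. That understates a rise, and it reverses the direction under the condition derived above. Over assumed factors of 2 to 10, the examples run from −33% against at least +33% to −80% against at least +100%. The low side is an inconsistency of scale by the factor DF, not a contradiction.

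The frequency is unknown and may be nil: the problem needs a diluted sample that is still out of range. The reach is limited. Biomarkers are exploratory, protocol 9.1 states no hypotheses, and dose escalation rests on safety, tolerability and PK (protocol 7.1.2). Primary safety and secondary PK results are untouched. The wording should still be corrected, because a literal implementation can give a wrong direction in a small arm without the footnote, and the correction needs no new data.

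**What to change.** In SAP 4.15, replace the two imputation bullets with:

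- Values reported as > ULOQ × dilution factor are replaced by ULOQ × dilution factor.
- Values reported as < LLOQ × dilution factor are replaced by (LLOQ × dilution factor)/2.
- The dilution factor is 1 for undiluted samples.

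The first line removes the error; the second puts the low side on the same scale. Keep the out-of-range counts, plot symbol, footnote, 50% rule and listings as planned.

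The cost is two lines of wording and the matching derivation code. The scaled limit is already part of the reported result. If the SAP is already final, section 1 provides for later changes through the Statistical Method Modification Form. If the scaled limit was intended all along, the edit only confirms it.

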1. Disease activity data (ACR20/50/70, DAS28, CDAI, SDAI, and blood sampling for ESR), blood for clinical laboratory tests, blood for biomarker assessments, and blood for possible future PD assessments will be collected prior to dosing on Day 1. Blood sampling for ESR will be collected and assessed at local laboratory.
2. Disease activity data (ACR20/50/70, DAS28, CDAI, SDAI, and blood sampling for ESR), blood for biomarker assessments, and blood for possible future PD assessments will be collected prior to dosing on Day 7 only. Blood sampling for ESR will be collected and assessed at local laboratory.
3. A full physical examination will be performed at the Screening Visit, Day 14, and Early termination visit; a brief physical will be performed on Days -1 and 10.
4. Blood for clinical laboratory tests will be withdrawn once on Days 4 and 7.
5. Vital signs will be collected at pre-dose and 1, 2, 4, 8, and 12 hours after dosing on Day 1.
6. 12-lead ECG will be conducted before blood sampling.
7. 12-lead ECG will be repeated once for eligibility confirmation at Screening and Day -1.
8. 12-lead ECG will be recorded at baseline and at 1, 2, 4, and 8 hours after dosing on Days 1 and 7.
9. Starting 2 hours prior to dosing and until 12 hours after dosing on Days 1 and 7.
10. Blood for PK sample analysis to determine parent and its metabolite concentrations and for possible future metabolite assessments will be sampled at pre-dose and 0.25, 0.5, 1, 1.5, 2, 3, 4, 6, 8, 12, 16, and 24 hours (pre-dose of Day 2) after dosing on Day 1, pre-dose on Days 3, 4, 5, 6, and on 7 at pre-dose and 0.25, 0.5, 1, 1.5, 2, 3, 4, 6, 8, 12, 16, 24, 48, and 72 hours after dosing on Day 7 (the sampling time points may be adjusted based on the PK results obtained from the previous parts or cohorts). The last dose will be administered on Day 7.
11. Urine for PK sample analysis will be collected at 0 (pre-dose) to 6, 6 to 12, and 12 to 24 hours after dosing on Day 1, and from 0 (pre-dose) to 6, 6 to 12, 12 to 24, 24 to 48, and 48 to 72 hours after dosing on Day 7. Urine collection intervals may be adjusted based on the PK results obtained from the previous parts or cohorts, e.g., if plasma PK sampling times are adjusted, the urine sampling times will be updated.
12. Sample will be obtained only from patients that consent to pharmacogenomics sampling.

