Exploratory 
● To evaluate the effect of TCK-276 on disease activity and biomarkers in patients with RA	
● Exploratory endpoints 
The following exploratory disease activity parameters for RA will be assessed:
 
○ American College of Rheumatology (ACR) 20/50/70 response criteria○ Disease activity score 28 (DAS28)○ Clinical disease activity index (CDAI)○ Simplified disease activity index (SDAI) 
The following exploratory biomarkers will be assessed:
 
○ Matrix metalloproteinase-3 (MMP-3)○ Granulocyte macrophage colony-stimulating factor (GM-CSF)○ C-X-C motif chemokine ligand 10 (CXCL10)○ C-C motif chemokine ligand 2 (CCL2)○ Cartilage oligomeric matrix protein (COMP)○ Tumor necrosis factor (TNF)-alpha○ TNF-R1○ Interleukin-6 (IL-6)

4 Study Design

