3 INVESTIGATIONAL PLAN

3.1 Overall Study Design and Plan

This is a Phase 1, multi-center, double-blind, randomized, placebo-controlled, multiple ascending dose (MAD) study to evaluate the safety, tolerability, and pharmacokinetics (PK) of orally administered TCK-276 in both males and females with RA. Blood samples for possible future pharmacogenetic, possible future metabolite assessments, and possible future pharmacodynamic (PD) assessments will be collected.

A total of thirty-two (32) patients with RA will be enrolled in this clinical study. This MAD study will consist of 4 cohorts of 8 patients (6 active treatment and 2 matching placebo, or a 3:1 ratio), each receiving an oral dose of TCK-276 or matching placebo for 7 days (once daily [QD] under fed condition). Each cohort will be divided into 2 subgroups to implement the sentinel dosing approach. Within each cohort, the first subgroup will consist of 2 sentinel patients; one patient will receive TCK-276, and one patient will receive matching placebo. The second subgroup will consist of 6 patients (5 active treatment, 1 matching placebo). Individual patients in the second subgroup will be dosed at least 72 hours after the first subgroup following a decision by the Investigators based on all available safety data from the sentinel patients up to 48 hours post-dose.

Dose group	Treatment Assignment	
1	10 mg TCK-276 (N = 6)	Placebo $(N = 2)$
2	25 mg TCK-276 (N = 6)	Placebo $(N = 2)$
3	75 mg TCK-276 (N = 6)	Placebo $(N = 2)$
4	175 mg TCK-276 (N = 6)	Placebo $(N = 2)$

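### SAP 4.15 withholds the out-of-range counts along with the means once over 50% of a biomarker's pooled values are imputed, so in markers already often out of range a strong drug effect can remove the table that would show it

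*SAP*

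**What the plan says.** The exploratory objective (Protocol Section 3, Table 3-1) is "To evaluate the effect of TCK-276 on disease activity and biomarkers in patients with RA". Eight biomarkers are named. Each is sampled twice (Protocol 1.3, footnotes 1 and 2): "blood for biomarker assessments, and blood for possible future PD assessments will be collected prior to dosing on Day 1", and then "blood for biomarker assessments, and blood for possible future PD assessments will be collected prior to dosing on Day 7 only".

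SAP 4.15 handles values outside the assay range in four steps.

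- **Imputation.** "Values below the LLOQ are replaced by LLOQ/2"; values above the ULOQ are set to the ULOQ.
- **Counts.** The out-of-range counts are rows of the same table as the means: "summary table, the frequency (n, %) of values below the LLOQ and above the ULOQ".
- **20% rule.** If more than 20% of values are imputed in any treatment group at any time point, the table stays and gains a footnote warning of bias.
- **50% rule.** "If the proportion of imputed data for a given biomarker, across all treatment groups and time points, is more than 50%, no summary statistics" are produced. The values are then only listed, with out-of-range results marked as such.

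The 20% rule is judged within group and time point. The 50% rule is judged once per marker, over everything pooled. No fallback table of counts is specified for a marker that fails it.

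**The concern.** When a drug lowers a marker, the share of values below the LLOQ is itself a result. The 50% rule uses that share, pooled with baseline and placebo, to decide whether anything is tabulated. The decision is therefore partly outcome-dependent.

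Heavy imputation is a good reason not to print a mean or SD, because those would rest largely on the constant LLOQ/2. It is no reason to withhold a count: n (%) below the LLOQ is valid at any degree of censoring, and it is the natural summary when censoring is heavy. The rule drops both together.

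At stake is a descriptive result. A shift from quantifiable on Day 1 to below the LLOQ on Day 7, graded by dose, would be a clear signal in a study whose results are meant to inform later dose selection (Protocol 2.1). For some markers that signal could be left in a patient listing with no by-group summary.

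**Working it through.** **Inputs.** SAP 3.1: "This MAD study will consist of 4 cohorts of 8 patients (6 active treatment and 2 matching placebo, or a 3:1 ratio"), and "A total of thirty-two (32) patients with RA will be enrolled in this clinical study". Two sampling days come from Protocol 1.3, and the threshold of more than 50% from SAP 4.15. The documents give no LLOQ and no expected out-of-range rate, so the background rate *b* below is an assumption shown over a range.

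**Step 1: the plan's own figure.** 4 × (6 + 2) = 32 patients, of whom 4 × 6 = 24 are active and 4 × 2 = 8 placebo. This reproduces the stated total.

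**Step 2: values per marker.** 32 × 2 = 64, made up of 32 on Day 1 before any drug, 8 placebo on Day 7 and 24 active on Day 7. More than 50% means at least 33 of 64.

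**Step 3: can drug effect alone trigger the rule?** Only the 24 active Day 7 values can move with the drug. If all of them fall below the LLOQ and nothing else does, the share is 24/64 = 37.5%, and the table is kept with its footnote. With every placebo value missing, the share is 24/48 = 50.0%, still not more than 50%. So no.

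**Step 4: background needed to reach 33.** The count required among the remaining values is 33 − *s*, where *s* is the number of fully suppressed active Day 7 values.

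| Cohorts fully suppressed | *s* | Others needed out of range |
|---|---|---|
| All four | 24 | 9 of 40 (22.5%) |
| Top three | 18 | 15 of 46 (32.6%) |
| Top two | 12 | 21 of 52 (40.4%) |
| Top one | 6 | 27 of 58 (46.6%) |

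**Step 5: partial suppression.** If 25%, 30% or 40% of the 40 values the drug cannot affect are out of range (10, 12 or 16 values), the table is lost once 23, 21 or 17 of the 24 active Day 7 values are out of range: 33 − 10, 33 − 12, 33 − 16.

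**Step 6: chance of losing the table.** This is a binomial tail at rate *b*: P(X ≥ 9), X ~ Bin(40, *b*), for full suppression; P(X ≥ 21), X ~ Bin(52, *b*), for the top two cohorts only; P(X ≥ 33), X ~ Bin(64, *b*), for no effect. Values are treated as independent, which is an approximation because each patient contributes two.

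| *b* | All active suppressed | Top two cohorts only | No drug effect |
|---|---|---|---|
| 10% | 0.016 | 0.0000 | 0.0000 |
| 20% | 0.41 | 0.0006 | 0.0000 |
| 25% | 0.70 | 0.011 | 0.0000 |
| 30% | 0.89 | 0.072 | 0.0003 |
| 40% | 0.99 | 0.53 | 0.040 |
| 50% | 1.00 | 0.94 | 0.45 |

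The same counts apply above the ULOQ for a marker that the drug raises.

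**The case against.** The case against giving this weight has four parts.

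1. **Assay sensitivity is the main driver.** A reader might infer that any drug strong enough to push a marker below the LLOQ deletes its table. Step 3 shows otherwise: a fully suppressed marker that is quantifiable elsewhere keeps its table. Conversely, a marker with no drug effect but mostly out-of-range values loses it. This stands. Drug effect decides only in a middle band of background rates.
2. **Suppression at every dose is a demanding assumption.** Cohorts 1 and 2, which hold 12 of the 24 active patients, receive 10 and 25 mg, below the projected effective dose of 75 mg (Protocol 4.3). Reaching 21 of 24 needs at least 9 of those 12 to be suppressed. This stands too, and the top-two-cohorts column is the fairer guide if only higher doses act.
3. **Nothing is erased.** All values stay in the listing, flagged, and a reader could count 64 of them by hand. True, but a by-group count should not depend on the reader doing that.
4. **The endpoint is exploratory.** Protocol 9.1 states no hypotheses, and the biomarker output is descriptive. This limits the consequence.

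A reader might also infer that conclusions on MMP-3, IL-6, TNF-alpha or GM-CSF will be biased toward no effect. The documents do not support that. They give no LLOQs or background rates for these markers, so it is not known whether any of them lies in the affected band.

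**Conclusion.** The concern holds in a conditional form. Above 50% pooled imputation, SAP 4.15 withholds the out-of-range counts as well as the means, and 24 of the 64 values entering that decision can carry the drug effect. The drug effect cannot trigger the rule by itself. It can tip the balance when roughly 20-40% of baseline and placebo values are already out of range and suppression extends across all doses, or at about 40% and above when only the top two cohorts respond. At a 30% background, for example, the chance of losing the table is about 0.89 with full suppression and 0.0003 with no effect.

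These figures assume that all 64 values are available, that no cohort is expanded, added or stopped and no patient replaced, and that values are independent. The loss is of a descriptive table for an exploratory objective; no primary or secondary result is affected. The change is nonetheless worth making, because it costs almost nothing and keeps a summary that stays valid under heavy censoring.

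**What to change.** In SAP 4.15, restrict the 50% rule to means, SDs and change-from-baseline statistics. Add one sentence: whatever the imputed share, n (%) below the LLOQ and n (%) above the ULOQ will be tabulated by treatment group and day, with each patient's shift between Day 1 and Day 7 (in range or out of range).

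Basing the 50% rule on Day 1 values alone is not recommended. It would remove the outcome dependence, but it could print Day 7 means built mostly from LLOQ/2. Nor is a new provision for medians needed, since SAP 4.2.6 already includes them in the standard summary.

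Cost: one SAP sentence and one small table per affected marker, with no new data. If the SAP is already final, its Section 1 provides a modification form for such changes.

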4.16 Adjustments for Covariates

Not Applicable

